10.3.3. Assessment Windows

Clinic visits are scheduled to take place as specified in [Appendix 2: Time & Events](#). Measurements outside visit windows will not be excluded from analyses. For all clinic visits, nominal visit days and times will be used for reporting, such that if a subject recorded values that were outside of the ± 7 day window for a visit they will still be reported under that visit.

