Part A Treatment: Those subjects meeting all of the inclusion/exclusion criteria by Visit 2 will receive mepolizumab 40 or 100 mg SC, depending on subject bodyweight (40 mg for subjects <40 kg and 100 mg for subjects \geq 40 kg). Subjects will receive their first dose of mepolizumab at Visit 2 and enter into the Treatment phase of the study. Subjects shall be observed for a minimum of 60 minutes in the clinic following each injection. Safety monitoring of subjects will occur during SC administration and for 1 hour after the three administrations in Part A and then follow monitoring policies for the center in Part B. Such monitoring will include general safety monitoring including monitoring for both systemic hypersensitivity (i.e., allergic/IgE-mediated and non-allergic) and local site reactions. In the event of an acute severe reaction (e.g., anaphylaxis) following administration of mepolizumab, there are personnel/staff onsite at the treatment facility who are appropriately trained in basic life support to manage the patient including administration of medications (e.g., epinephrine) and have access to a system that can promptly transport the patient to another facility for additional care if appropriate.

Those subjects who enter the run-in period but do not meet all inclusion/exclusion criteria will be deemed Run-in failures and will not be dosed in the study. The reason for any Run-in failure will be recorded in the eCRF.

During the Part A Treatment phase, all subjects will receive mepolizumab either 40mg (subjects <40kg at Visit 2) or 100 mg SC (subjects \geq 40kg at Visit 2) at week 0 (Visit 2), week 4 (Visit 3) and week 8 (Visit 4) which will provide therapeutic coverage through to week 12 (Visit 6/End of Therapy Visit). Visit 6 will mark the end of the treatment phase.

Subjects will visit the clinic at week 9 (Visit 5) to allow for measurement of the approximate peak mepolizumab concentration.

Part A Follow-up: Following completion of Visit 6, subjects will enter into the Follow-up phase which will consist of two additional visits at weeks 16 (Visit 7) and 20 (Visit 8).

Long-Term Safety / Long Term Pharmacodynamic Phase (Part B)

Treatment Arm	SC dose

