5.5. Withdrawal/Stopping Criteria

Subjects may be withdrawn from study treatment at anytime by the Investigator if it is considered to be detrimental for them to continue in the study. Reasons for withdrawal can include: an adverse event (including abnormal liver function test or abnormal laboratory results), lost to follow-up, protocol violation, lack of efficacy, sponsor terminated study, non-compliance, pregnancy, or for any other reason.

Liver chemistry stopping criteria are detailed in Section [5.5.1](#)

Subjects are also free to withdraw consent to participate in the study at anytime. Every effort should be made to have them return to the clinic for an Early Withdrawal Visit (See [Table 3](#) and [Table 4](#)) and to return all study related materials. In those instances where the subject specifies the reason for withdrawal of consent, this information will be captured in the eCRF.

A subject should only be designated as lost to follow-up if the site is unable to establish contact with the subject after 3 documented attempts via 2 different methods (phone, text, e-mail, certified letter, etc).

[figure not shown]
For both Part A and Part B of this study an Exit Visit should be conducted within 4 weeks of the last dose received. In the event that a subject withdraws at, or during, a scheduled visit, an Early Withdrawal Visit should be performed at this visit instead. A Follow-up Visit should then be scheduled 12 weeks after the last dose of investigational product (Visit 8 or Visit 23 for subjects withdrawing from study Parts A or B, respectively).

Any data collected up until the point of withdrawal will be used in the analyses.

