 2. For subjects who had a positive anti-mepolizumab antibody response at the 12 week post-last-dose follow-up assessment (Visit 8) (or last study visit at which immunogenicity was assessed if the Follow-up (Visit 8) immunogenicity sample is not available) an attempt will be made to obtain a serum sample for anti-mepolizumab antibodies at least 4 months after the last dose of study drug in Part A or upon completion of Part A, whichever is later.
 3. Exit visit should be performed as close as possible to the planned week 12 visit date.
 4. Therapy history to include a detailed review of prior biologics received for treatment of asthma, including prior investigational anti-IL5 or anti-IL13 preparations.
 5. During the treatment period, all lab samples and procedures should be obtained prior to study treatment administration.
 6. A positive Hepatitis B Surface Antigen and Hepatitis C antibody is exclusionary
 7. This immunogenicity sample must always be collected 12 weeks (\pm 7 days) post-last-dose of study treatment; therefore, for subjects who withdraw from study treatment early, this sample must be collected 12 weeks (\pm 7 days) after their confirmed last dose of study treatment (i.e., prior to Visit 8). In the event that this sample collection date coincides with an Early Withdrawal Visit, only one immunogenicity sample should be collected.
 8. Visit 8 to be performed 12 weeks post last dose. For subjects continuing into the long-term extension phase Part B, Visit 9 should be conducted on the same day as Visit 8 once all of the visit 8 assessments have been completed. Assessments performed at Visit 8 that are also listed for Visit 9 should not be duplicated if Visit 8 and Visit 9 are performed on the same day.

Table 4 Time and Events Table Long-Term Safety / Pharmacodynamic Phase (Part B)

Procedure	Eligibility Check / First Dose	Treatment Period													Exit Visit	Follow-up ³	Early Withdrawal
Visit	9	10	11	12	13	14	15	16	17	18	19	20	21	22	23		
Week of Study (visit window \pm 5 days)	20	24	28	32	36	40	44	48	52	56	60	64	68	72	80		
Subject Screen																	
Informed consent	X ¹																
Inclusion and exclusion criteria	X ¹																
Safety Assessments																	
Concomitant medications	X	X	X	X	X	X	X	X	X	X	X	X	X	X	X	X	
Hematology (including eosinophils) ²	X			X			X			X			X	X	X	X	
Clinical Chemistry ²	X			X			X			X			X	X		X	
12-lead ECG														X		X	
Vital signs	X	X	X	X	X	X	X	X	X	X	X	X	X	X	X	X	

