10.3.4. Early Withdrawal Visits

If a subject withdraws from the study at a scheduled visit (i.e. completes an Early Withdrawal Visit), where endpoint data were scheduled to be collected, the data will be summarised and analysed (as appropriate) together with data from subjects who did not withdraw from the study. If a subject withdraws from the study at a scheduled visit at which endpoint data were not scheduled to be collected, or if a subject withdraws

between scheduled visits, data will be slotted to the nearest adjacent visit where the endpoint data was scheduled to be collected (if data at that visit were not recorded) according to the Time and Events schedule ([Appendix 2: Time & Events](#)).

For example, if a subject prematurely withdraws from the study and completed the Early Withdrawal Visit at Visit 5 (Week 9) and completes an Early Withdrawal Visit which includes an FEV1 assessment, the FEV1 data collected will need to be re-assigned to an adjacent visit where FEV1 data is scheduled for collection. In this case the FEV1 data will be reassigned to Visit 4 (Week 8) (if data at that visit were not recorded) as this is the closest nominal visit at which collection of FEV1 data is scheduled.

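### SAP 10.3.3 reports an early stopper's 12-week post-dose follow-up as Week 20 or Week 80 whatever its date, so those rows mix study weeks and numbers of doses received

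*SAP*

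**What the plan says.** **Timing.** Part A doses are given "at week 0 (Visit 2), week 4 (Visit 3) and week 8 (Visit 4"), and Visit 8 is nominally Week 20. In Part B, Table 4 schedules doses every 4 weeks from Week 20 (Visit 9) to Week 68 (Visit 21), and Visit 23 is nominally Week 80.

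**Follow-up of a child who stops early.** Protocol 5.5 schedules it "12 weeks after the last dose of investigational product (Visit 8 or Visit 23 for subjects withdrawing from study Parts A or B, respectively"). Table 3 footnote 8 agrees for Part A: "Visit 8 to be performed 12 weeks post last dose". Footnote 7 reads differently. It asks for an early stopper's 12-week immunogenicity sample "after their confirmed last dose of study treatment (i.e., prior to Visit 8"), as though Visit 8 were a later occasion.

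**Reporting.** SAP 10.3.3 states: "For all clinic visits, nominal visit days and times will be used for reporting". Values outside the window stay where they are: "they will still be reported under that visit". SAP 10.5.3 repeats the nominal-visit rule for summary tables and summary figures. It keeps actual time for listings and individual figures.

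**Early Withdrawal values.** Under SAP 10.3.4 a value taken at a visit where that endpoint was due is used at that visit. Any other value is "slotted to the nearest adjacent visit where the endpoint data was scheduled to be collected (if data at that visit were not recorded"). No fallback is given for the case where that visit is already filled.

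**The concern.** The protocol fixes the date of Visit 8 and Visit 23 by the last dose, while the SAP fixes their label by the planned calendar. The two agree only for a child who received the last planned dose. For anyone who stopped sooner, a count or score from an earlier study week, after fewer doses, goes into the Week 20 or Week 80 row.

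Those rows carry named endpoints. Change in ACQ-7 and C-ACT at Week 20 is a Part A secondary endpoint. Change in eosinophils at Week 80 is a Part B secondary endpoint, and ACQ-7 and C-ACT at Week 80 are exploratory. Eosinophils are also summarised by visit in Part A, where Week 12 is the primary timepoint. A child whose only dose was at Week 0 would have a true Week 12 count shown at Week 20. With about 20 evaluable children and no hypothesis test, the by-visit rows are themselves the result that readers will use.

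**Working it through.** **1. Reproduce the plan's labels.** Follow-up week = week of last dose + 12.
- Part A, last planned dose at Week 8: 8 + 12 = 20, the nominal week of Visit 8.
- Part B, last planned dose at Week 68: 68 + 12 = 80, the nominal week of Visit 23.

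The labels are right for children who had the last planned dose.

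**2. Apply the same rule to early stoppers.** Label error = nominal week − (week of last dose + 12).

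| Part | Last dose (week) | True follow-up (week) | Reported as | Label late by (weeks) |
|---|---|---|---|---|
| A | 0 | 12 | 20 | 8 |
| A | 4 | 16 | 20 | 4 |
| A | 8 | 20 | 20 | 0 |
| B | 20 | 32 | 80 | 48 |
| B | 24 | 36 | 80 | 44 |
| B | 64 | 76 | 80 | 4 |
| B | 68 | 80 | 80 | 0 |

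Between the Part B lines shown, the error falls by 4 weeks for each further dose.

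**3. What is mixed and what is not.** In the Week 20 row, true study week can be 12, 16 or 20, after as few as one Part A dose. In the Week 80 row, true study week runs from 32 to 80, after 1 to 13 Part B doses, since (68 − 20)/4 + 1 = 13. Time since last dose is 12 weeks in every case.

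**4. Look for a rule that corrects it.**
- SAP 10.5.3 allows the impact of major timing deviations to be assessed, but a follow-up held as Protocol 5.5 directs need not count as a deviation.
- SAP 10.6.1 prefers the value closest to a window's target day, but the SAP tabulates no analysis windows.
- Listings show actual time, but the summary rows do not.

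**5. Early Withdrawal slotting.** The SAP's example reproduces. FEV1 taken at Week 9 is 1 week from Week 8 and 3 weeks from Week 12, so Week 8 is nearest. If the Week 8 value exists, as it normally would, the condition fails and no row is named.

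In Part B the eosinophil, ACQ-7 and C-ACT visits are Weeks 20, 32, 44, 56, 68, 72 and 80. Withdrawal at Weeks 24, 36, 48 or 60 is nearest to a visit already passed (20, 32, 44, 56). Withdrawal at Weeks 28, 40, 52 or 64 is nearest to the next one (32, 44, 56, 68). Section 10.3.5 cannot supply the missing rule: it claims similar logic for unscheduled visits but slots only where the visit already has data, which is the opposite condition.

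**6. How many children.** The only guide is the Part A allowance of 28 treated for 20 evaluable: 28 − 20 = 8, and 8/28 = 28.6%. Evaluability also fails for missed assessments, so not all 8 need be early stoppers. No early-stopping rate is given for Part B.

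**The case against.** The strongest reply is that everyone at Visit 8 or Visit 23 is 12 weeks past the last dose, so the row has a coherent meaning as a post-treatment follow-up. That stands. A reader might infer that the Week 20 row mixes different washout times, and it does not. What differs is study week and number of doses, which a row headed by a study week does not convey.

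Footnote 7 could also be read as keeping Visit 8 at Week 20 for early stoppers, which would remove most of the Part A problem. But it governs only the immunogenicity sample, and it conflicts with footnote 8 and Protocol 5.5. While that conflict remains, sites may label the same occasion differently.

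Three stronger readings are tempting, and the documents do not support them.
- *Early Withdrawal values are discarded.* No rule says so. SAP 10.7.1 lists all data from withdrawn children and includes available planned data in displays, and Protocol 5.5 uses data collected up to withdrawal. The fault is a missing fallback.
- *One third of Part B withdrawal visits lose their values.* That counts 4 of the 12 dosing visits from Week 24 to Week 68. It needs Visit 9 to count as filled, yet assessments done at Visit 8 are not repeated at Visit 9 on the same day. If Visit 9 is empty, the Week 24 value has a slot and the count is 3 of 12. Reading either count as a share of children also assumes withdrawals spread evenly over visits.
- *The Week 0 to 20 exacerbation summary treats early stoppers as observed for 20 weeks.* SAP 10.4.2 assigns exacerbations by actual dates, with separate definitions for early withdrawals, and a Kaplan-Meier summary of time to first exacerbation is planned. The nominal-visit rule does not reach these.

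**Conclusion.** The point holds for the follow-up label. As written, the protocol and SAP together report true Week 12 or 16 values at Week 20, and true Week 32 to 76 values at Week 80. The label is up to 8 weeks late in Part A and up to 48 weeks late in Part B. This assumes that sites follow Protocol 5.5 and footnote 8 when they name the visit.

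The effect is limited to by-visit descriptive summaries of eosinophils, ACQ-7 and C-ACT. Few children are likely to contribute, and nothing is formally tested. One qualification applies to Week 80: children moving to the long-term access program have no Visit 23. The row rests on the remaining children, so even one or two early stoppers could be a visible share of it. The documents do not say how many will move.

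The Early Withdrawal gap and the footnote conflict are secondary clarifications.

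**What to change.** In SAP 10.3.3, limit the Week 20 and Week 80 rows to children who received the last planned dose of that part (Week 8 or Week 68). Report early stoppers' Visit 8 or Visit 23 in a separate row, '12 weeks after last dose (early stoppers)', with actual study day. Base the rule on receipt of the last planned dose and not on a count of doses. A count of fewer than 3 or 13 would remove a child who missed a middle dose but had a correctly timed visit.

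In SAP 10.3.4, state that an Early Withdrawal value whose nearest scheduled visit is filled goes into a separate Early Withdrawal row with actual study day. Do not move it to the next visit: Part B values from Weeks 24, 36, 48 and 60 would then appear at Weeks 32, 44, 56 and 68, each 8 weeks late.

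Reconcile Table 3 footnote 7 with footnote 8 and Protocol 5.5 on when Visit 8 occurs for an early stopper.

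The cost is SAP wording, two extra table rows and one protocol footnote. The downside is a slightly smaller n in the Week 20 and Week 80 rows. A one-dose child's true Week 12 count would appear in the separate row and not at the primary timepoint, but its actual study day would be visible.

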10.3.4. Early Withdrawal Visits

If a subject withdraws from the study at a scheduled visit (i.e. completes an Early Withdrawal Visit), where endpoint data were scheduled to be collected, the data will be summarised and analysed (as appropriate) together with data from subjects who did not withdraw from the study. If a subject withdraws from the study at a scheduled visit at which endpoint data were not scheduled to be collected, or if a subject withdraws

between scheduled visits, data will be slotted to the nearest adjacent visit where the endpoint data was scheduled to be collected (if data at that visit were not recorded) according to the Time and Events schedule ([Appendix 2: Time & Events](#)).

For example, if a subject prematurely withdraws from the study and completed the Early Withdrawal Visit at Visit 5 (Week 9) and completes an Early Withdrawal Visit which includes an FEV1 assessment, the FEV1 data collected will need to be re-assigned to an adjacent visit where FEV1 data is scheduled for collection. In this case the FEV1 data will be reassigned to Visit 4 (Week 8) (if data at that visit were not recorded) as this is the closest nominal visit at which collection of FEV1 data is scheduled.

10.3.5. Unscheduled Visits

For unscheduled visits, similar logic will be applied. If a subject has an unscheduled assessment then this data would be slotted to the closest adjacent scheduled visit but only if information already exists at that visit. If an unscheduled visit occurred between two scheduled visits for which data has been reported, then the data from the unscheduled visit will remain in the unscheduled visit and will not be used in summary tables and analyses (except for endpoints using any post-baseline data) but will be presented in any relevant listings.

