4.3. Type and Number of Subjects

Approximately 40 male or female subjects with severe eosinophilic asthma, aged 6 to 11 years inclusive at screening (Visit 1), will be screened to achieve approximately 28 eligible subjects entering the Part A treatment phase to allow availability of 20 evaluable subjects, with a minimum of six subjects enrolled in the < 40 kg bodyweight group. An evaluable subject is defined to be a subject who has received all three doses of mepolizumab and has all PK and PD assessments completed through to Visit 6 (week 12).

Sample size is not determined for Part B. All subjects who completed Part A and meet the eligibility criteria for Part B will be allowed to participate in Part B.

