7.2. Analysis of Blood Eosinophil Count (Part A)

The blood eosinophil count (primary PD endpoint in this study) is recorded during the laboratory investigations under hematology data at the visits indicated in the [Appendix 2: Time & Events](#). Week 12 is the primary timepoint of interest for blood eosinophil count and ratio of blood eosinophil count to baseline.

The absolute blood eosinophil count, and ratio to baseline will be summarised using geometric mean and other descriptive statistics and listed for each mepolizumab dose and overall by visit for the PDe population. Additionally the geometric mean ratio to baseline in blood eosinophil count (including 95% CI) for each mepolizumab dose and overall by visit will be presented graphically. See details of the summary statistics in Section 10.5.3.

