
 • Reporting for tables and figures : 
 • Nominal visits (planned time relative to dosing) will be used in summary figures and summary tables. Actual time relative to dosing will be used in individual subject figures. • The impact of any major deviation from the planned assessment times and/or scheduled visit days on the analyses and interpretation of the results will be assessed as appropriate. • Reporting for Data Listings: 
 • Planned and actual time relative to study drug dosing will be shown in listings (Refer to IDSL Statistical Principle 5.05.1). • Unscheduled or unplanned readings will be presented within the subject data listings • Scheduled visits outside the protocol defined time-windows (i.e. recorded as protocol deviations) will be included in listings, summaries and statistical analyses. The impact of any major deviation from the planned assessment times and/or scheduled visit days on the summaries, figures, analyses will be assessed as appropriate.
Unscheduled Visits

 • When possible unscheduled assessments will be slotted to the closest adjacent scheduled visit. If an unscheduled visit occurs between two completed scheduled visits, the data from the unscheduled visit will not be used in summary tables which are based on by-visit assessments. The information from the unscheduled visit will be included in 'any time post-baseline' summaries and will also be presented in any relevant listings. See Section 10.3 for further details.

Reporting Standards	
Descriptive Summary Statistics	
Continuous Data	Refer to IDSL Statistical Principle 6.06.1
Categorical Data	N (number of subjects in the treatment group), n (number of subjects with non-missing values), frequency, %
Reporting of Pharmacokinetic Concentration Data	
Descriptive Summary Statistics	Refer to IDSL Statistical Principle 6.06.1 Refer to GUI_51487 for further details of handling NQ/BQL values
Reporting of Pharmacokinetic Parameters	

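### SAP 10.3.5 states the condition for slotting unscheduled data the wrong way round, and 10.5.3 does not correct it

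*SAP*

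**What the plan says.** Three places in the SAP bear on where off-schedule data go.

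- **10.3.4 (early withdrawal).** Data collected off schedule move to the nearest visit at which the endpoint was due, on the condition "if data at that visit were not recorded) according to the Time and Events schedule". The worked example, FEV1 moved from Visit 5 to Visit 4, repeats that condition.
- **10.3.5 (unscheduled visits).** It opens with "For unscheduled visits, similar logic will be applied". Its second sentence then has the data "slotted to the closest adjacent scheduled visit but only if information already exists at that visit". Its third sentence covers an unscheduled visit between two scheduled visits that both have reported data: "the data from the unscheduled visit will remain in the unscheduled visit and will not be used in summary tables". Listings and endpoints that use any post-baseline value are exempt.
- **10.5.3 (reporting standards).** "When possible unscheduled assessments will be slotted to the closest adjacent scheduled visit". Then: "If an unscheduled visit occurs between two completed scheduled visits, the data from the unscheduled visit will not be used in summary tables", meaning tables built on by-visit assessments. It sends the reader to Section 10.3 for detail.

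Two other sections matter. SAP 10.6.1 says what happens when a visit holds several values: a mean is taken, or within a time window the value closest to the target day, with the mean if they are equally distant. SAP 7.2 names week 12 as the main timepoint for blood eosinophils, the primary pharmacodynamic endpoint, and has the count and its ratio to baseline summarised and "listed for each mepolizumab dose and overall by visit for the PDe population".

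**The concern.** The rule decides which values enter the by-visit tables and figures. In 10.3.5 the operative condition is the opposite of the one it claims to mirror. A programmer who follows the sentence as written and one who follows the stated analogy with 10.3.4 would build different by-visit datasets, and each could point to the SAP.

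Two things could go wrong on the literal text. A visit with no value stays empty although an unscheduled value lies next to it. And a visit that already has its scheduled value can receive a second one, so that 10.6.1 comes into play and an observed scheduled value may be averaged with, or displaced by, an unscheduled one. The by-visit summaries of eosinophils, ACQ-7, C-ACT and FEV1 are all exposed. No hypothesis is tested, so what is at stake is estimates and confidence intervals; in a study that takes an estimation approach, those are the results.

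**Working it through.** **1. The rules side by side.** For an unscheduled value, call the nearer scheduled visit N and the other neighbouring scheduled visit O. A visit can be completed and still lack the value, for instance when a blood sample fails, so completed and has data are kept apart.

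| Situation | Logic of 10.3.4 | 10.3.5, second sentence | 10.3.5, third sentence | 10.5.3, literal |
|---|---|---|---|---|
| N and O both have data | do not slot | slot | do not slot | do not use |
| N has data; O completed, value missing | do not slot | slot | silent | do not use |
| N has data; O not completed | do not slot | slot | silent | slot when possible |
| N and O completed; value missing at N | slot | do not slot | silent | do not use |
| Value missing at N; at least one of N and O not completed | slot | do not slot | silent | slot when possible |

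Three things follow.

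- The second sentence of 10.3.5 gives the opposite answer to 10.3.4 in every row.
- In the first row 10.3.5 contradicts itself, unless its third sentence is taken as an exception to the second.
- 10.5.3 does not restore the 10.3.4 logic. In the fourth row it keeps the value out of by-visit tables where 10.3.4 would use it. In the third row, read literally, it slots where 10.3.4 would not.

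**2. A concrete case.** Suppose the week 12 eosinophil sample fails, a repeat is drawn a few days later and recorded as unscheduled, and the week 16 visit takes place. The 10.3.4 logic fills week 12. The second sentence of 10.3.5 does not, because nothing is recorded at week 12. Nor does 10.5.3, because both visits were completed.

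**3. Illustration of size.** Inputs: log-scale SD 0.7867 (Protocol 9.2); 28 subjects entering treatment (Protocol 4.3); and 6 for the lighter group, "with a minimum of six subjects enrolled in the < 40 kg bodyweight group" (Protocol 4.3). Treating 0.7867 as the SD of the log ratio to baseline, as the protocol does, the 95% limits are the estimate divided and multiplied by

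exp( t(0.975, n−1) × 0.7867 / √n ).

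Check against the protocol's own example, 20 subjects and a ratio of 0.14: exp(2.0930 × 0.7867 / √20) = 1.445. The limits are 0.14 / 1.445 = 0.097 and 0.14 × 1.445 = 0.202. The protocol gives 0.09 to 0.20, so the formula agrees apart from rounding of the lower limit.

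Now suppose one week 12 value is left out that could have been filled:

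- n = 28: exp(2.0518 × 0.7867 / √28) = 1.357. n = 27: exp(2.0555 × 0.7867 / √27) = 1.365. Change: 1.3651 / 1.3567 = 1.006, or 0.6%.
- n = 6: exp(2.5706 × 0.7867 / √6) = 2.283. n = 5: exp(2.7764 × 0.7867 / √5) = 2.656. Change: 2.6560 / 2.2832 = 1.163, or 16%.

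The effect of adding a second value to an occupied visit was not sized; it depends on the values themselves.

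**The case against.** The best defence is that this is a dropped negative and that no careful reader would be misled. The stated analogy with 10.3.4, the condition given twice there, and the third sentence of 10.3.5 all point to filling empty visits only. That is very likely the intent. It does not make the sentence right: the section devoted to unscheduled visits gives the reverse instruction, and a pre-specified rule should not depend on the reader supplying a missing word.

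Other points limit the harm.

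- 10.6.1 says how several values at one visit are handled. That settles which number is used once a second value has been slotted; it does not justify slotting it.
- 10.3.3 keeps out-of-window scheduled visits under their nominal label, so late visits do not become unscheduled. This stands, and it reduces the number of values affected.
- An evaluable subject has, by definition, all pharmacodynamic assessments through Visit 6, so the 20 evaluable subjects have no week 12 gap to fill. This also stands. However, SAP 7.2 summarises the wider PDe population. And an evaluable subject could still receive a second week 12 value if an unscheduled sample falls just after week 12 and the week 16 value is missing.

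A reader might also infer that 10.5.3 sets up a separate, third rule. The documents do not support that. It is a short reporting convention that defers to 10.3; if its opening words mean that the visit is empty, and completed means data reported, it is a vaguer form of 10.3.4. The sound criticism is that it is too loose to repair 10.3.5. Nor is an empty visit left unfilled only by 10.3.5: the fourth row of the table shows 10.5.3 doing the same.

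**Conclusion.** The point holds. SAP 10.3.5 states its slotting condition in reverse of the section it says it follows, and conflicts with its own next sentence when both neighbouring visits have data. SAP 10.5.3 does not resolve this. It is an error in an operative data rule rather than a missing detail, and the wording should be corrected.

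The reversal rests on the text alone. The size does not: the documents give no number of unscheduled samples, so the total effect cannot be computed and is probably small. The 0.6% and 16% figures assume one lost week 12 value, a log SD of 0.7867, and 28 or 6 subjects who would otherwise have a value. The 16% further assumes a dose group at its enrolment minimum, so it is not a forecast.

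A reader might go on to conclude that the primary pharmacodynamic result is unreliable, or take the number of situations in which the texts disagree as a measure of impact. Neither follows. The disagreements are logical possibilities, not frequencies, and listings and any-time-post-baseline summaries are unaffected.

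**What to change.** Make these changes before the database freeze for the reporting effort concerned.

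- **10.3.5, second sentence.** Replace the condition with: *only if data for that endpoint were not recorded at that visit; otherwise the value remains unscheduled and is used only in any-time-post-baseline summaries and listings.*
- **10.5.3, first sentence on unscheduled visits.** Replace the opening words *When possible* with the same condition.
- **10.5.3, second sentence.** Change *two completed scheduled visits* to *two scheduled visits with data recorded for that endpoint*. Without this change, a completed week 12 visit with a failed eosinophil sample would still be treated differently in 10.3.5 and 10.5.3.

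The cost is one clause in 10.3.5 and two in 10.5.3. No new data, analyses or outputs are needed.
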